15 APPENDICES

Appendix 1 Neurostatus® scoring sheet

neurostatus scoring

Scoring Sheet for a standardised, quantified neurological examination and assessment of Kurtzke's Functional Systems and Expanded Disability Status Scale in Multiple Sclerosis

STUDY NAME		SYNOPSIS									
PERSONAL INFORMATION		1. Visual	Ambulation Score								
Patient											
Date of Birth (04-Jun-1980)											
Centre Nr/Country		EDSS Step									
Name of EDSS rater		2. Brainstem									
Date of Examination											
		3. Pyramidal									
		4. Cerebellar									
		5. Sensory									
		6. Bowel/Bladder									
		7. Cerebral									
		Signature									
1. VISUAL (OPTIC) FUNCTIONS											
OPTIC FUNCTIONS		OD	OS	Scotoma							
Visual acuity	 CC  SC										
Visual fields											
2. BRAINSTEM FUNCTIONS		* Disc pallor									
CRANIAL NERVE EXAMINATION		FUNCTIONAL SYSTEM SCORE									
Extraocular movements (EOM) impairment											
Nystagmus											
Trigeminal damage											
Facial weakness											
3. PYRAMIDAL FUNCTIONS		Hearing loss									
REFLEXES		R	> <	L	Dysarthria						
Biceps											
Triceps											
Brachioradialis											
Knee											
Ankle:											
Plantar response											
Cutaneous reflexes											
* Palmonatal reflex											
LIMB STRENGTH		R	> <	L	Dysphagia						
Deltoid											
Biceps											
Triceps											
Wrist/finger flexors											
Wrist/finger extensors											
Hip flexors											
Knee flexors											
Knee extensors											
Plantar flexion (feet/toes)											
Dorsiflexion (feet/toes)											
* Position test UE, pronation											
* Position test UE, downward drift											
* Position test LE, sinking											
* Able to lift only one leg at a time (grade in *)											
* Walking on heels											
* Walking on toes											
* Hopping on one foot											
SPASTICITY											
Arms											
Legs											
Gait											
OVERALL MOTOR PERFORMANCE											
FUNCTIONAL SYSTEM SCORE											

CC = corrected
 SC = without correction

* = optional part of the examination
 1 = converted FS Score

4. CEREBELLAR FUNCTIONS

CEREBELLAR EXAMINATION			
Head tremor		Rapid alternating movements UE impairment	
Truncal ataxia		Rapid alternating movements LE impairment	
		R	L
Tremor/dysmetria UE		Tandem walking	
Tremor/dysmetria LE		Gait ataxia	
		Romberg test	
		Other, e. g. rebound	
		FUNCTIONAL SYSTEM SCORE	

5. SENSORY FUNCTIONS

SENSORY EXAMINATION		R	L		
Superficial sensation UE				Position sense UE	
Superficial sensation trunk				Position sense LE	
Superficial sensation LE				* Lhermitte's sign	
Vibration sense UE				* Paraesthesiae UE	
Vibration sense LE				* Paraesthesiae trunk	
				* Paraesthesiae LE	
		FUNCTIONAL SYSTEM SCORE			

6. BOWEL/ BLADDER FUNCTIONS

Urinary hesitancy/retention		Bowel dysfunction	
Urinary urgency/incontinence		* Sexual dysfunction	
Bladder catheterisation		FUNCTIONAL SYSTEM SCORE	

→ ¹

7. CEREBRAL FUNCTIONS

MENTAL STATUS EXAMINATION			
* Depression		Decrease in mentation	
* Euphoria		* Fatigue	
		FUNCTIONAL SYSTEM SCORE	

AMBULATION

Distance reported by patient (in meters)		Assistance	
Time reported by patient (in minutes)		Distance measured (in meters)	
		AMBULATION SCORE	

* = optional part of the examination

¹ = converted FS Score

* Depression and Euphoria are not taken into consideration for FS and EDSS calculation.

* Because fatigue is difficult to evaluate objectively, in some studies it does not contribute to the Cerebral FS score or EDSS step. Please adhere to the study's specific instructions.

UE = upper extremities

LE = lower extremities

Appendix 2 Diagnostic criteria for MS (2010 Revised McDonald Criteria)

Clinical Presentation	Additional Data Needed for MS Diagnosis
≥ 2 attacks ^a ; objective clinical evidence of ≥ 2 lesions or objective clinical evidence of 1 lesion with reasonable historical evidence of a prior attack ^b	None ^c
≥ 2 attacks ^a ; objective clinical evidence of 1 lesion	Dissemination in space, demonstrated by: ≥ 1 T2 lesion in at least 2 of 4 MS-typical regions of the CNS (periventricular, juxtacortical, infratentorial, or spinal cord) ^d ; or Await a further clinical attack ^a implicating a different CNS site
1 attack ^a ; objective clinical evidence of ≥ 2 lesions	Dissemination in time, demonstrated by: Simultaneous presence of asymptomatic gadolinium-enhancing and non-enhancing lesions at any time; or A new T2 and/or gadolinium-enhancing lesion(s) on follow-up MRI, irrespective of its timing with reference to a baseline scan; or Await a second clinical attack ^a
1 attack ^a ; objective clinical evidence of 1 lesion (clinically isolated syndrome)	Dissemination in space and time, demonstrated by: For dissemination in space (DIS): ≥ 1 T2 lesion in at least 2 of 4 MS-typical regions of the CNS (periventricular, juxtacortical, infratentorial, or spinal cord); or Await a second clinical attack ^a implicating a different CNS site; and For dissemination in time (DIT): Simultaneous presence of asymptomatic gadolinium-enhancing and non-enhancing lesions at any time; or A new T2 and/or gadolinium-enhancing lesion(s) on follow-up MRI, irrespective of its timing with reference to a baseline scan; or Await a second clinical attack ^a
Insidious neurological progression suggestive of MS (PPMS)	1 year of disease progression (retrospectively or prospectively determined) plus 2 of 3 of the following criteria ^d : 1. Evidence for DIS in the brain based on ≥ 1 T2 lesions in the MS-characteristic (periventricular, juxtacortical, or infratentorial) regions 2. Evidence for DIS in the spinal cord based on ≥ 2 T2 lesions in the cord 3. Positive CSF (isoelectric focusing evidence of oligoclonal bands and/or elevated IgG index)

If the criteria are fulfilled and there is no better explanation for the clinical presentation, the diagnosis is “MS”; if suspicious, but if the criteria are not completely met, the diagnosis is “possible MS”; if another diagnosis arises during the evaluation that better explains the clinical presentation, then the diagnosis is “not MS”.

^aAn attack (relapse; exacerbation) is defined as patient-reported or objectively observed events typical of an acute inflammatory demyelinating event in the CNS, current or

historical, with duration of at least 24 hours, in the absence of fever or infection. It should be documented by contemporaneous neurological examination, but some historical events with symptoms and evolution characteristic for MS, for which no objective neurological findings are documented, can provide reasonable evidence of a prior demyelinating event. Reports of paroxysmal symptoms (historical or current) should, however, consist of multiple episodes occurring over not less than 24 hours. Before a definite diagnosis of MS can be made, at least 1 attack must be corroborated by findings on neurological examination, visual evoked potential response in subjects reporting prior visual disturbance, or MRI consistent with demyelination in the area of the CNS implicated in the historical report of neurological symptoms.

^bClinical diagnosis based on objective clinical findings for 2 attacks is most secure. Reasonable historical evidence for 1 past attack, in the absence of documented objective neurological findings, can include historical events with symptoms and evolution characteristics for a prior inflammatory demyelinating event; at least 1 attack, however, must be supported by objective findings.

^cNo additional tests are required. However, it is desirable that any diagnosis of MS be made with access to imaging based on these criteria. If imaging or other tests (for instance, CSF) are undertaken and are negative, extreme caution needs to be taken before making a diagnosis of MS, and alternative diagnoses must be considered. There must be no better explanation for the clinical presentation, and objective evidence must be present to support a diagnosis of MS.

^dGadolinium-enhancing lesions are not required; symptomatic lesions are excluded from consideration in subjects with brainstem or spinal cord syndromes.

MS = multiple sclerosis; CNS = central nervous system; MRI = magnetic resonance imaging; DIS = dissemination in space; DIT = dissemination in time; PPMS = primary progressive multiple sclerosis; CSF = cerebrospinal fluid; IgG = immunoglobulin G.

[\[Polman 2011\]](#)

Appendix 3 Prohibited anti-arrhythmic and HR-lowering drugs

The following anti-arrhythmic and HR-lowering drugs (systemic administration) are prohibited during the study [see Section 5.2.6]:

- Adenosine
- Acebutolol
- Ajmaline
- Amiodarone
- Aprinidine
- Atenolol
- Azimilide
- Bepridil
- Betaxolol
- Bisoprolol
- Bretylium
- Bunaftine
- Carvedilol
- Cibenzoline
- Disopyramide
- Dofetilide
- Dronedarone
- Encainide
- Esmolol
- Flecainide
- Ibutilide
- Ivabradine
- Lidocaine
- Lorajmine
- Lorcainide
- Metoprolol
- Mexiletine
- Moracizine
- Nadolol
- Phenytoin
- Pilocarpine
- Prajmaline
- Procainamide
- Propafenone
- Propranolol
- Quinidine
- Sotalol
- Sparteine
- Tedisamil
- Timolol
- Tocainide
- Vernakalant

If, in the judgment of the investigator, it is in the best interests of the subject to receive any of the drugs listed above, study drug must be permanently discontinued. This list is not exhaustive, other anti-arrhythmic or HR-lowering drugs are also prohibited. In case of doubt, please discuss with the sponsor the use of any potential anti-arrhythmic or HR-lowering drug.

Appendix 4 Guidance for concomitant treatment with QT-prolonging drugs with known risk of Torsades de Pointes

QT-prolonging medications with known risk of Torsades de Pointes (e.g., azithromycin, citalopram, clarithromycin, erythromycin, escitalopram, moxifloxacin, etc.) should be administered with caution since ponesimod may potentially enhance their effect on QT interval. A list of QT-prolonging medications with known risk of TdP is published by AZCERT [University of Arizona CERT <http://crediblemeds.org/>]. The investigator should also take into account other relevant risk factors such as hypokalemia when considering treatment with a QT-prolonging drug. If treatment with such drugs is considered necessary, the principal investigator / treating neurologist should always discuss with the first-dose administrator and/or a cardiologist the appropriateness of combining such drugs with the study drug and may interrupt or permanently discontinue study drug. If the principal investigator determines in the best interest of the subject to concomitantly administer a QT-prolonging drug with known risk of Torsades de Pointes the following recommendations must be adhered to:

- a) For a need to start treatment or to increase the dose of a QT-prolonging drug with known risk of Torsades de Pointes during the up-titration, treatment with study drug must be interrupted.
- Study drug can only be re-initiated [see Section 5.1.9] after the QT-prolonging drug has been stopped or once the QT-prolonging drug has reached the steady-state.
 - Once the QT-prolonging drug has reached the steady-state and prior to re-initiation of study drug, the QTcF interval obtained pre-dose on the day of the planned re-initiation must be \leq 450 ms for males or \leq 470 ms for females.
 - Following re-initiation of study drug, at next visit (scheduled or unscheduled occurring after completion of the up-titration), perform ECG measurements pre-dose.
- b) For a need to start treatment or to increase the dose of a QT-prolonging drug with known risk of Torsades de Pointes during the study excluding the up-titration (i.e., after 2 weeks of study drug initiation or re-initiation).
- At visit (scheduled or unscheduled) prior to initiation or dose increase of QT-prolonging drug with known risk of Torsades de Pointes, perform ECGs measurements pre-dose.
 - If prior to initiation or dose increase of QT-prolonging drug with known risk of Torsades de Pointes, the QTcF interval is $>$ 450 ms for males or $>$ 470 ms for females, treatment with study drug must be interrupted.

- At next visit (scheduled or unscheduled occurring once the QT-prolonging drug has reached the steady-state [approximately after 5 half-lives of the QT-prolonging drug]) following initiation or dose increase of QT-prolonging drug with known risk of Torsades de Pointes, perform ECGs measurements pre-dose.

Appendix 5 Adverse events of special interest

Adverse events of special interest (AESIs) will include the anticipated risks of treatment with ponesimod and the events that may be related to MS comorbidities (e.g., seizures or stroke), and will address the following safety areas:

- Effect on heart rate and rhythm AESIs (including hypotension)
- Hepatobiliary disorders / Liver enzyme abnormality AESIs
- Pulmonary AESIs
- Macular edema AESIs
- Infection AESIs
- Herpetic infection AESIs
- Skin malignancy AESIs
- Non-skin malignancy related AESIs
- Cardiovascular AESIs
- Hypertension AESIs
- Stroke AESIs
- Seizure AESIs

A list of AESIs (MedDRA preferred terms) will be defined in the SAP.

Appendix 6 Abnormalities for ECG, BP and laboratory variables

Notable abnormalities for ECG and BP that are related to the potential effects of ponesimod will address the following variables:

- Morphological ECG findings (defined as any abnormal finding not present prior to start of treatment).
- HR outliers (bpm), based on ECG
- PR interval (ms)
- QT/QTc interval (ms), QTcB or QTcF
- BP (mmHg)

The definition of the abnormal values to be reported will be described in the SAP.

Laboratory abnormalities

Laboratory values below or above the normal range will be graded at three levels (H, HH, HHH for values above normal range and L, LL, LLL for values below the normal range) where L stands for “low”, H for “high”.

The term “marked abnormality” describes laboratory values above or below the thresholds, with grading of abnormalities at two levels: LL/HH and LLL/HHH. These thresholds have been defined by the sponsor in order to flag and/or communicate abnormal laboratory results from the central laboratory to the investigators, and for the purpose of standardized data analysis and reporting by the sponsor. The definitions of marked abnormal values are based mainly on the Common Terminology Criteria for Adverse Events (CTCAE) [[CTCAE 2010](#)] grading system and, in specific cases (e.g., lymphocyte levels), are adjusted based on the known PD effect of the study drugs (e.g., LLL threshold for lymphocytes).

The term ALERT here corresponds to protocol-defined test result threshold requiring an action from the investigator as described in the protocol (e.g., repeat the test; interrupt or discontinue the study drug) and should not be confused with the term “call alert” used by the central laboratory for laboratory results, which will be communicated to the investigator. Not all ALERTS listed in this table will be “call alerts” from the central laboratory and vice versa.

PLEASE NOTE: Thresholds for abnormality of level L or H are not provided in this appendix but will be provided in the central laboratory manual. Parameters for which no threshold is defined in the table below may be defined in the central laboratory manual.

Thresholds for marked laboratory abnormalities

Parameter (SI unit)	LL	LLL	HH	HHH
Hemoglobin (g/L)	< 100	< 80	Increase in > 20 g/L above ULN or above baseline (if baseline is above ULN)	Increase in > 40 g/L above ULN or above baseline (if baseline is above ULN)
MCH (pg/Cell)	ND	ND	ND	ND
MCV (fL)	ND	ND	ND	ND
Hematocrit (L/L)	< 0.28 (female) < 0.32 (male)	< 0.20	> 0.55 (female) > 0.60 (male)	> 0.65
Platelet count (10^9 /L)	< 75	< 50	> 600	> 999
RBC count (10^{12} /L)	ND	ND	ND	ND
WBC count (10^9 /L)	NA	< 1.9	> 20.0 ALERT: > 20.0	> 100.0
Lymphocyte (10^9 /L)	ND	< 0.2 ALERT: < 0.2 Decrease of > 50 % from the value of total lymphocyte count recorded at Visit 5 (Week 4) associated with a total lymphocyte count < 0.5×10^9/L recorded at two consecutive visits after Visit 5 (Week 4)	> 4.0	≥ 8
Neutrophils (10^9 /L)	< 1.5	< 1.0	ND	ND

Parameter (SI unit)	LL	LLL	HH	HHH
Eosinophils (10^9 /L)	ND	ND	> 5.0	ND
Monocytes (10^9 /L)	ND	ND	ND	ND
Basophils (10^9 /L)	ND	ND	ND	ND
Polymorphonuclear leucocyte/Band cells (%)	ND	ND	> 90%	> 95%
AST (U/L)*	ND	ND	≥ 3 ULN ALERT: ≥ 3 ULN	≥ 5 ULN ALERT: ≥ 5 ULN ≥ 8 ULN
ALT (U/L)*	ND	ND	≥ 3 ULN ALERT: ≥ 3 ULN	≥ 5 ULN ALERT: ≥ 5 ULN ≥ 8 ULN
Total bilirubin (umol/L)	ND	ND	≥ 2 ULN ALERT: ≥ 2 ULN combined with ALT or AST ≥ 3 ULN	≥ 5 ULN
Alkaline Phosphatase (U/L)	ND	ND	> 2.5 ULN	> 5 ULN
INR*	ND	ND	> 1.5 ULN or > 1.5 times above baseline if on anticoagulation ALERT: > 1.5 combined with ALT or AST ≥ 3 ULN	> 2.5 ULN or > 2.5 times above baseline if on anticoagulation
Lactate dehydrogenase	ND	ND	ND	ND
Creatinine (umol/L)*	ND	ND	>1.5 ULN or >1.5 x baseline	> 3 ULN or >3 x baseline
Creatinine clearance (mL/min)	< 60	< 30	ND	ND
Urea (mmol/L)	ND	ND	> 2.5 ULN	> 5 ULN

Confidential

Parameter (SI unit)	LL	LLL	HH	HHH
Albumin (g/L)	< 30	< 20	ND	ND
Protein total (g/L)	ND	ND	ND	ND
C-reactive protein (mg/L)	ND	ND	ND	ND
Glucose (mmol/L)	< 3.0	< 2.2	> 8.9	> 13.9
Potassium (mmol/L)	< 3.2	< 3.0	> 5.5	> 6.0
Sodium (mmol/L)	ND	< 130	> 150	> 155
Calcium (mmol/L)	< 2.0	< 1.75	> 2.9	> 3.1
Chloride (mmol/L)	ND	ND	ND	ND
Triglyceride (mmol/L)	ND	ND	> 3.42	> 11.4
Cholesterol (mmol/L)	ND	ND	> 7.75	> 12.92
Serum pregnancy test	ND	ND	ND	Positive ALERT: Positive

* HH and HHH based on CTCAE 2010 v4.03 [[CTCAE 2010](#)]. An ALERT will be sent when INR \geq 1.5 based on the guidance for monitoring liver test abnormalities from FDA [[FDA 2009b](#)]

ALERT = study-specific alerts that trigger specific actions by the investigator [see Section [7.3.13.1](#)]; ALT = alanine aminotransferase; AST = aspartate aminotransferase; NA = not applicable; INR = International Normalized Ratio; MCH = mean corpuscular hemoglobin; MCV = mean corpuscular volume; ND = not defined; may be complemented by definitions provided by the central laboratory (see central laboratory manual); RBC = red blood count; SI = international system of units; ULN = upper limit of normal; WBC = white blood cell.

Appendix 7 Multiple Sclerosis Functional Composite

The MSFC consists of the three following assessments:

1) Timed 25-Foot walk;

The Timed 25-Foot Walk is a quantitative measure of lower extremity function. It is the first component of the MSFC administered at each visit. The subject is directed to one end of a clearly marked 25-foot course and is instructed to walk 25 feet as quickly as possible, but safely. The task is immediately administered again by having the subject walk back the same distance. Subjects may use assistive devices when doing this task. In clinical trials, it is recommended that the treating neurologist select the appropriate assistive device for each subject.

2) 9-Hole Peg Test (9-HPT);

The 9-HPT is a quantitative measure of upper extremity (arm and hand) function. The 9-HPT is the second component of the MSFC to be administered. Both the dominant and non-dominant hands are tested twice (two consecutive trials of the dominant hand, followed immediately by two consecutive trials of the non-dominant hand). It is important that the 9-HPT be administered on a solid table (not a rolling hospital bedside table) and that the 9-HPT apparatus be anchored.

3) Paced Auditory Serial Addition Test (PASAT-3" version).

The PASAT is a measure of cognitive function that specifically assesses auditory information processing speed and flexibility, as well as calculation ability. The PASAT is presented on audiocassette tape or compact disc to control the rate of stimulus presentation. Single digits are presented every 3 seconds and the subject must add each new digit to the one immediately prior to it. The test score is the number of correct sums given (out of 60 possible) in each trial. To minimize familiarity with stimulus items in clinical trials and other serial studies, two alternate forms have been developed; the order of these should be counterbalanced across testing sessions. The PASAT is the last measure of the MSFC that is administered at each visit.

Test administration:

The MSFC should be administered as close to the beginning of a study visit as possible but definitely before the subject does a distance walk. MSFC components should be administered in the following order:

1. Trial 1, Timed 25-Foot Walk
2. Trial 2, Timed 25-Foot Walk

3. Trial 1, Dominant Hand, 9-HPT
4. Trial 2, Dominant Hand, 9-HPT
5. Trial 1, Non-Dominant Hand, 9-HPT
6. Trial 2, Non-Dominant Hand, 9-HPT
7. PASAT-3”

Scoring:

There are three components to the MSFC: (1) the average scores from the four trials on the 9-HPT (the two trials for each hand are averaged, converted to the reciprocals of the mean times for each hand and then the two reciprocals are averaged); (2) the average scores of two Timed 25-Foot Walk trials; (3) the number correct from the PASAT-3. The MSFC is based on the concept that scores for these three dimensions – arm, leg, and cognitive function – are combined to create a single score (the MSFC) that can be used to detect change over time in a group of MS subjects. This is done by creating Z-scores for each component of the MSFC.

$$\text{MSFC Score} = \{Z_{\text{arm, average}} + Z_{\text{leg, average}} + Z_{\text{cognitive}}\} / 3.0$$

Where $Z_{\text{xxx}} = Z\text{-score}$

Nine Hole Peg Test

Name: _____

Dominant Hand (circle one): Right Left

Time to complete the test in seconds:

Date: _____ Dominant Hand: _____ Non-Dominant Hand: _____

PASAT - Form A

Name _____ Date _____

PRACTICE

9+1	3	5	2	6	4	9	7	1	4
10	4	8	7	8	10	13	16	8	5

RATE #1
(3'')

1+4	8	1	5	1	3	7	2	6	9
5	12	9	6	6	4	10	9	8	15
4	7	3	5	3	6	8	2	5	1
13	11	10	8	8	9	14	10	7	6
5	4	6	3	8	1	7	4	9	3
6	9	10	9	11	9	8	11	13	12
7	2	6	9	5	2	4	8	3	1
10	9	8	15	14	7	6	12	11	4
8	5	7	1	8	2	4	9	7	9
9	13	12	8	9	10	6	13	16	16
3	1	5	7	4	8	1	3	8	2
12	4	6	12	11	12	9	4	11	10

Total Correct (raw) = _____ Percent Correct = _____

PASAT - Form B

Name _____ Date _____

PRACTICE	9+1	3	5	2	6	4	9	7	1	4
	10	4	8	7	8	10	13	16	8	5

RATE #1 (3'')	2+7	5	8	2	9	6	4	1	3	6
	9	12	13	10	11	15	10	5	4	9
	3	6	2	8	4	9	1	6	7	2
	9	9	8	10	12	13	10	7	13	9
	4	1	5	7	3	9	7	2	6	8
	6	5	6	12	10	12	16	9	8	14
	4	2	5	8	5	9	3	7	1	4
	12	6	7	13	13	14	12	10	8	5
	2	4	3	6	1	7	3	8	3	9
	6	6	7	9	7	8	10	11	11	12
	1	3	5	2	6	4	9	7	1	4
	10	4	8	7	8	10	13	16	8	5

Total Correct (raw) = _____ Percent Correct = _____

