- Change in MSFC Z-score from baseline by visit up to EOS;
- Change in the SDMT score from baseline by visit up to EOS;
- Change from baseline by visit up to EOS in fatigue-related impacts as measured by the impact sub-scales of the FSIQ-RMS.

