3. PASAT
4. SDMT

A full description of the administration of the scale, sequence of tests and scoring will be given in a separate document provided to each site. The test administrator will be trained on the test administration before the initiation of the site. The test will only be administered by a trained administrator.

A more comprehensive description of the test and its administration is provided in [Appendix 7](#).

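### Appendix 7 adds the Timed 25-Foot Walk Z-score to the MSFC without reversing its direction, so under the printed rule slower walking raises an exploratory composite in which higher otherwise means better

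*Protocol*

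**What the plan says.** Section 6.1.3 of the Protocol lists among the other clinical exploratory endpoints "Change in MSFC Z-score from baseline by visit up to EOS". Section 11.3.4.6 compares the arms on it by ANOVA, and Section 11.3.4 sets an exploratory two-sided 0.05 level.

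The scoring rule is in Appendix 7:

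- **Arm (9-Hole Peg Test).** The two trials for each hand are averaged, then "converted to the reciprocals of the mean times for each hand and then the two reciprocals are averaged".
- **Leg and cognitive.** These are "2) the average scores of two Timed 25-Foot Walk trials; (3) the number correct from the PASAT-3".
- **Combination.** "This is done by creating Z-scores for each component of the MSFC". The composite is the arm, leg and cognitive Z-scores added together and divided by 3.0. The symbol Z is explained only as a Z-score.

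Appendix 7 also describes the tasks. In the walk, the subject is "instructed to walk 25 feet as quickly as possible, but safely". For the PASAT, "The test score is the number of correct sums given (out of 60 possible) in each trial".

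Section 7.2.4 says that a full account of administration, "sequence of tests and scoring will be given in a separate document provided to each site", and refers to Appendix 7 for a more comprehensive description of the test. The site document is not available here.

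**The concern.** Two of the three tests are timed, and on a timed test a larger value means worse function. Appendix 7 deals with this for the arm by taking reciprocals and does nothing comparable for the leg. It then adds the leg term with the same sign as two terms for which larger is better. Sections 6.1.3, 7.2.4 and 11.3.4.6 and the rest of Appendix 7 neither reverse the walk term nor say which direction of the composite is favourable.

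At stake is the reading of one exploratory endpoint. If the rule were programmed as printed, a treatment benefit confined to walking would appear as a loss of function, and a benefit across all three domains would be understated. Because the arm reciprocal is spelled out, a programmer working from the text could reasonably conclude that the leg needs no transformation.

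**Working it through.** The Protocol gives no power or effect-size figure for the MSFC, so there is no planned figure to reproduce. The check concerns direction.

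**Direction of each input (Appendix 7)**

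| Component | Quantity entered | When function worsens |
|---|---|---|
| Arm | Mean of reciprocals of time | Falls |
| Leg | Average of two timed walks | Rises |
| Cognitive | Number correct out of 60 | Falls |

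**Formula.** The ordinary Z-score is Z = (x - reference mean) / reference SD. It keeps the direction of x for any mean and any positive SD. Let a, w and c be the worsening, in SD units, of arm, walking and cognition.

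- Change as printed: (-a + w - c) / 3
- Change with the walk term reversed: (-a - w - c) / 3
- Gap between the two: 2w / 3

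When there is net worsening overall, the printed result has the wrong sign whenever w exceeds a + c.

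**Illustrative values (not trial figures)**

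| Worsening (a, w, c) | As printed | Walk reversed |
|---|---|---|
| 0.3, 0.3, 0.3 | (-0.3 + 0.3 - 0.3)/3 = -0.10 | (-0.3 - 0.3 - 0.3)/3 = -0.30 |
| 0, 0.6, 0 | +0.6/3 = +0.20 | -0.6/3 = -0.20 |
| 1, 1, 1 | (-1 + 1 - 1)/3 = -0.33 | (-1 - 1 - 1)/3 = -1.00 |

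With equal changes, the leg term cancels one of the other two components, and one third of the intended change remains.

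**In seconds.** The Protocol gives no reference mean or SD for the walk, so these are assumed over a range. A walk 20% slower than the mean changes Z by 0.2 × mean / SD, and the composite by one third of that.

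| Assumed mean, SD (s) | Walk Z | MSFC as printed | Walk reversed |
|---|---|---|---|
| 5.5, 1.5 | 1.1/1.5 = 0.733 | +0.244 | -0.244 |
| 6, 2 | 1.2/2 = 0.600 | +0.200 | -0.200 |
| 8, 4 | 1.6/4 = 0.400 | +0.133 | -0.133 |
| 9.5, 11 | 1.9/11 = 0.173 | +0.058 | -0.058 |

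The size depends on the assumed reference values; the sign does not.

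**The case against.** The strongest reply is that Appendix 7 is not the operative derivation. Section 11 gives the algorithms for derivations to the SAP, Section 11.2 leaves the definition of exploratory variables to it, and Section 7.2.4 places the scoring in a separate site document. Appendix 7 gives no reference mean, SD or population, so no MSFC value can be computed from it alone. The sign could be set where those are supplied. The walk Z-score is never written out, and the text speaks of average scores rather than seconds, so reading it as raw time is an inference, though a natural one for a timed test.

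Much of this stands as a limit on the point. A reader might infer that the trial's MSFC values are, or will be, wrong at every visit. The documents do not support that, because the derivation actually used is not shown. Section 7.2.4 also has the test results recorded on a source form and transferred to the eCRF, so the composite can be derived with the right sign later.

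The deferral does not remove the point. Appendix 7 is not silent: it prints a formula and corrects direction for one timed test but not the other. With Z-score in its ordinary meaning, a correct SAP would have to depart from the Protocol text.

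**Conclusion.** The point holds as a defect in the printed definition. Under the ordinary meaning of Z-score, and with the walk scored as time, slower walking raises the MSFC. For equal changes in all three components the composite keeps one third of the intended change. When walking alone changes, its sign is reversed.

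Two stronger readings should be resisted:

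- **That the walk term cancels both other components.** With equal changes it cancels one, which is why -0.10 remains rather than zero or a positive value.
- **That the trial's conclusion on disability is at risk.** Disability is tested through 12-week confirmed accumulation on the EDSS, which has its own ambulation scoring (Section 7.2.1). The MSFC is outside the testing hierarchy. The primary endpoint, the five secondary endpoints and the sample size do not use it.

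This is worth correcting because the text gives a wrong result when followed, but its reach is one exploratory endpoint.

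**What to change.** In Appendix 7, write out the leg term as Z_leg = -(mean walk time - reference mean) / reference SD, and state there that a higher MSFC means better function. Check that the site scoring document and the SAP derivation use the same sign. The cost is one sign and one sentence; assessments, data collection and testing are unchanged.
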